Study 2: Translation and Validation of the Thai Version of the Foot Function Index (FFI-Th)

Study Protocol

This study employed a cross-sectional design to adapt and validate the Foot Function Index (FFI) into Thai (FFI-Th). The translation process followed internationally recommended cross-cultural adaptation guidelines. Initially, two bilingual translators independently performed forward translations from English to Thai, which were then synthesized by an expert committee into a single version. This was back-translated into English by two native English speakers fluent in Thai to check for consistency. The pre-final Thai version was harmonized through consensus among health professionals, followed by cognitive interviews with 20 individuals to ensure clarity and cultural relevance. The final version was proofread by a linguist before use.

Participants included adults who could read and understand Thai and reported foot problems. A minimum sample size of 48 participants was determined based on prior reliability studies of similar FFI versions. Data were collected using the FFI-Th questionnaire, along with the EQ-5D-5L (a quality of life measure) and a pain visual analogue scale (pain-VAS).

Statistical Analysis Plan

Data analysis was conducted using SPSS software with significance set at $p < 0.05$. Descriptive statistics summarized demographic characteristics and questionnaire scores. The study examined floor and ceiling effects to identify items with extreme response patterns and noted the frequency of “not applicable” responses.

The reliability of the FFI-Th was assessed: internal consistency was evaluated using Cronbach's alpha, with values above 0.7 indicating acceptable consistency. Test-retest reliability was measured by the intraclass correlation coefficient (ICC) from repeated assessments one week apart, with ICC values interpreted as poor (<0.5), moderate (0.5–0.75), good (0.75–0.9), or excellent (>0.9).

Construct validity was explored through Principal Component Analysis (PCA) using varimax rotation, retaining factors with eigenvalues greater than 1 to confirm the underlying questionnaire structure. Criterion validity was assessed by correlating the FFI-Th scores with both the pain-VAS and EQ-5D-5L using Pearson's correlation coefficient. Correlation strengths were interpreted as weak (<0.3), moderate (0.3–0.5), or strong (>0.5), with positive or negative values indicating the direction of the relationship.

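### Study 2 asks an eigenvalue-above-1 PCA to confirm the FFI-Th structure, but it states no structure to confirm and the data set the number of components, so the analysis can only explore

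*Combined protocol and SAP*

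**What the plan says.** In the Study 2 Statistical Analysis Plan, the construct-validity sentence opens with "Construct validity was explored through Principal Component Analysis (PCA) using varimax rotation" and ends with "retaining factors with eigenvalues greater than 1 to confirm the underlying questionnaire structure". It gives no expected number of factors, no allocation of items to subscales, no loading criterion and no confirmatory factor model. The number of items is not stated either.

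The Study 2 Study Protocol says: "A minimum sample size of 48 participants was determined based on prior reliability studies of similar FFI versions". No separate sample-size basis is given for the PCA. The plan also expects that items may pile up at the ends of the scale: "The study examined floor and ceiling effects to identify items with extreme response patterns". It will record how often items are marked not applicable, but does not say how such answers enter the PCA.

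**The concern.** To confirm a structure, one must state it beforehand and some result must be able to count against it. Here the data choose the number of components and nothing is written down for comparison, so no outcome would be a failure to confirm. Exploring and confirming are different claims, and the sentence makes both.

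The second issue is how reliable the rule is. The eigenvalue-above-1 criterion is applied to sample eigenvalues, which spread around their population values. In a small sample, components that are only noise can rise above 1, and real but correlated factors can fall below it. If that happens, the reported number of Thai subscales, and the grouping of items into them, is weak evidence in either direction. Construct validity is one of the properties that Study 2 sets out to establish.

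**Working it through.** **1. The plan's own figure.** The 48 cannot be reproduced, because no target ICC, null ICC, interval width or power is given. As a plausibility check with two ratings, the Walter-Eliasziw-Donner formula is k = 1 + 4(zα + zβ)² / (ln C)², with C = [1 + 2ρ0/(1−ρ0)] / [1 + 2ρ1/(1−ρ1)]. For assumed ICCs of 0.6 against 0.8, two-sided 0.05 and 80% power, C = 4/9, (ln C)² = 0.658, and k = 1 + 4(7.85)/0.658 = 48.7, so 49. Bonett's width formula with ICC 0.75 and width 0.25 also gives 49. So 48 is a plausible size for reliability. Neither calculation bears on component extraction.

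**2. Inputs for the PCA.** From the document: minimum n = 48, PCA, varimax, eigenvalue above 1. Assumed, because the document is silent: three true factors, 15 to 23 items (5/5/5, 6/6/6 or 9/9/5), equal loadings λ, factor correlation φ of 0.3 to 0.7, normal items.

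**3. Population eigenvalues.** With three equal subscales of m items, the second and third eigenvalues are 1 + (m−1)λ² − mλ²φ, and all after the third are 1 − λ². For m = 5, λ = 0.6:
- φ = 0.3: 1 + 1.44 − 0.54 = 1.90
- φ = 0.7: 1 + 1.44 − 1.26 = 1.18
- remaining 12 eigenvalues: 1 − 0.36 = 0.64

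So in the population the rule gives exactly three; any error comes from sampling.

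**4. Why n = 48 causes trouble.** A rough upper edge for the sample noise eigenvalues is (1 − λ²)(1 + √(p/n))², for p items. With p = 15 and n = 48 the second factor is (1 + 0.559)² = 2.43. The edge is 0.64 × 2.43 = 1.56 at λ = 0.6, 0.51 × 2.43 = 1.24 at 0.7, and 0.36 × 2.43 = 0.87 at 0.8. Only the last is below 1. With p = 23, n = 200 and λ = 0.7 it is 0.51 × 1.79 = 0.91.

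**5. Simulation: share of samples keeping more than three components.**

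| n | λ = 0.6 | λ = 0.7 | λ = 0.8 |
|---|---|---|---|
| 48 | 85-100% | 28-98% | 0-14% |
| 100 | 51-100% | 1-42% | 0% |
| 200 | 5-75% | 0% | 0% |

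With 30% of answers at the lowest score and n = 48, the first row becomes 96-100%, 56-100% and 3-51%.

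**6. Outside that range of items.** With 30 items and λ = 0.8, the number is wrong in 48-62% of samples at n = 48 (two or three true factors). With 12 items, three factors and φ = 0.7, the rule keeps too few in 46-53% at λ of 0.8 to 0.9; at 0.8 the third population eigenvalue is only 1 + 1.92 − 1.79 = 1.13. With 12 items at λ = 0.7 the error is smaller, 13-36%.

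**7. Would obtaining three components confirm three factors?** Share of samples with exactly three, n = 48:

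| Setting | Three true | Two true | One true |
|---|---|---|---|
| 15 items, λ = 0.6 | 3-10% | 16-21% | 36-40% |
| 18 items, λ = 0.7 | 26-32% | 45-49% | 35-37% |
| 15 items, λ = 0.7 | 56-62% | 47-51% | 19-25% |
| λ = 0.8 | 81-100% | 1-20% | 0-6% |

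In the first two rows, a count of three is likelier under a different structure. At 0.8 it is informative.

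**8. Usable n.** If 1-2% of answers per item are not applicable, independently across items, and incomplete cases are dropped, then 48 × 0.99¹⁵ = 41 and 48 × 0.98²³ = 30. Both conditions are assumptions. If such answers cluster in the same people, the loss is smaller.

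**The case against.** The strongest reply has four parts.

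- **The document is a summary of work on a named, existing instrument.** The structure meant may simply be that of the source FFI, and a fuller protocol may list it. This stands in part. Naming the subscales elsewhere would supply something to compare against, but a data-driven count would still not be a confirmatory test.
- **48 is a minimum, and item count, loadings and achieved n are unknown.** This stands. A reader might infer that the component count in this study will be wrong, or that 48 is too few for Study 2. The documents support neither. The error rate runs from near 0% to 100% over plausible inputs, and 48 is reasonable for the reliability aim.
- **High loadings would remove the problem.** Often true, but not generally, as the 30-item and 12-item results show.
- **Fixing the number of components has its own bias.** This stands, and it shapes the fix. A reader might infer that the fixed solution should replace the eigenvalue rule, since it groups items better in simulations with three true factors. That advantage is built in, because those simulations assume that the fixed number is correct. When one intended subscale is really two factors correlated 0.6 to 0.7, agreement of a three-component solution with the wrong intended structure is still about 93-98% at loadings of 0.7 and 96-100% at 0.8 (n = 48). At 0.8 the eigenvalue count exceeds three in 55-100% of such samples, against 0-16% when three is true.

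**Conclusion.** The wording point holds without any simulation: an analysis with no stated structure and a data-chosen number of components can explore but not confirm, and the sentence contradicts itself.

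The numerical point holds conditionally. If achieved n is near 48 and loadings are about 0.6 to 0.7 with 15 to 23 items, the number of components is often wrong, mostly too high, and even the expected count may say little. If n is much larger with loadings of 0.7 or more, mainly the claim of confirmation remains at issue. The documents do not allow the study to be placed in this range.

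This should be corrected, but it is confined to the structure claim. A reader might infer that the FFI-Th is unsound as a whole; nothing here supports that. Cronbach's alpha, the test-retest ICC, the correlations with pain-VAS and EQ-5D-5L, and Studies 1 and 3 do not depend on the PCA.

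**What to change.** 1. Replace *confirm* with *explore* and limit the conclusion to exploratory evidence, unless a confirmatory factor model with its own sample-size justification is fitted.
2. Name the subscales of the source FFI and the items in each, taken from the instrument and not from the results. Add a PCA with the number of components fixed at that number.
3. Report the fixed and eigenvalue-based solutions side by side, neither demoted. Give item agreement with the intended subscales descriptively, with no pass mark, and state the n used and how not-applicable answers were handled.

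The two solutions are needed together because they detect different errors. If two intended subscales are really one factor, fixed-solution agreement at n = 48 averages 59-69% at loadings of 0.6 and 64-70% at 0.7 to 0.8, against 74-97%, 89-100% and 98-100% at 0.6, 0.7 and 0.8 when the intended structure is true. If one subscale is really two correlated factors, agreement barely moves, and the eigenvalue count is what can reveal it when loadings are high.

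The cost is wording and one standard SPSS option on the same data, and it can be added after the analysis. The downsides to state are a more modest structure claim, and that high agreement from the fixed solution is weak evidence on its own.

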Study 3: Effects of Strengthening and Stretching Exercise Programs on Pain and Gait in Patients with Plantar Fasciitis: A Randomized Controlled Trial

Study Protocol

This study was a double-blind randomized controlled trial conducted at Physical Therapy Center, Mahidol University. It aimed to compare the effects of strengthening versus stretching exercises on individuals with PF.

Participants were diagnosed with PF based on clinical symptoms and ultrasound measurement, and then were randomly allocated into two groups: strengthening and stretching. Both groups initially received standardized conservative physical therapy (therapeutic ultrasound and manual therapy) twice a week for 4 weeks. Subsequently, they followed their assigned home-based exercise program three days a week for 4 weeks, continuing independently for 2 months after supervised intervention ended. Participants and the physical therapist who provided a conservative PT intervention were blinded to group allocation.

Outcome assessments, including pain intensity via visual analog scale (VAS) and gait parameters measured on a force distribution platform, were performed at five time points: Baseline, 2 weeks after the intervention, 4 weeks after the intervention, 1-month follow-up, 2-month follow-up

Statistical Analysis Plan

Data distribution was tested for normality using the Kolmogorov-Smirnov test. Outcome measures were analyzed using two-way repeated measures ANOVA to examine:

- Main effects of time (changes across assessment points),
- Main effects of group (differences between strengthening and stretching groups),
- Interaction effects (whether changes over time differed by group).

Post-hoc Bonferroni tests identified specific time points with significant differences. Independent sample t-tests compared groups at individual assessment times. Statistical significance was set at $p < 0.05$. SPSS software was used for all analyses.

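### Study 3 plans a repeated measures ANOVA over five assessments with no analysis set or missing-data rule; a mixed model with a pre-named covariance would use every observed value

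*Combined protocol and SAP*

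**What the plan says.** Study 3 is the randomised comparison of strengthening with stretching exercise. Under its Study Protocol heading, pain on a visual analogue scale and gait measures "were performed at five time points: Baseline, 2 weeks after the intervention, 4 weeks after the intervention, 1-month follow-up, 2-month follow-up". After the supervised phase, participants follow the exercise programme at home, "continuing independently for 2 months after supervised intervention ended".

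Under its Statistical Analysis Plan heading, "Outcome measures were analyzed using two-way repeated measures ANOVA to examine" three effects: time, group, and "Interaction effects (whether changes over time differed by group". Separately, "Independent sample t-tests compared groups at individual assessment times", and "SPSS software was used for all analyses".

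Neither heading says who is analysed (all randomised, per protocol or completers) or what happens to a participant with a missed visit. No imputation, sensitivity analysis or SPSS procedure is named. The nearest text elsewhere, on questionnaire items answered as not applicable, belongs to Study 2.

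**The concern.** A conventional repeated measures ANOVA needs a full row of five values per participant; a t-test at one visit needs only that visit. With nothing stated, the two between-group analyses may describe different sets of people, and the reader cannot tell.

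The interaction test is the plan's own test of whether change over time differs by arm. If incomplete cases are dropped, that test loses data already collected, and it no longer covers everyone randomised. It also generally needs a stronger missingness assumption than a likelihood-based mixed model, which is valid under missing at random. The two unsupervised months make missed late visits plausible.

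**Working it through.** **Inputs from the documents.** Two randomised arms; five assessments (baseline and four follow-ups); significance level 0.05; SPSS. Study 3 gives no sample size, power, effect size, SD or dropout rate, so there is no planned figure to reproduce. The minimum of 48 participants belongs to Study 2.

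**Assumptions, for illustration only.** Baseline always observed; missing completely at random; rate p = 5% or 10% per follow-up; 80% power for the interaction on full data. Three patterns: independent misses, monotone dropout (hazard p at each follow-up), or the same people missing all four follow-ups.

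**1. Participants left in a listwise ANOVA.** For independent misses and for monotone dropout the share is (1−p)^4: 0.95^4 = 0.8145 and 0.90^4 = 0.6561. For full overlap it is 0.95 and 0.90. With independent misses at 10%, a t-test at any follow-up uses 90% of participants and the ANOVA 65.6%.

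**2. Collected values discarded, independent misses.** The share of planned values observed is (1+4(1−p))/5, that is 0.96 and 0.92. The share discarded is 1 − 0.8145/0.96 = 15.2% and 1 − 0.6561/0.92 = 28.7%.

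**3. Interaction power, covariance treated as known.** With five visits the interaction has 4 df. The noncentrality for 80% power (chi-square, 4 df) is 11.935. Completers keep 11.935 × 0.8145 = 9.72 or 11.935 × 0.6561 = 7.83. The mixed model's information is the sum, over missingness patterns, of pattern probability times the inverse covariance of the observed visits. Ranges cover compound symmetry 0.4, 0.6, 0.8 and AR(1) 0.6, 0.8, each with five assumed shapes of group difference.

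| Pattern | Completers, 5% / 10% | Mixed model, 5% / 10% |
|---|---|---|
| Independent | 70.2% / 59.4% | 76.8–79.5% / 73.2–78.9% |
| Monotone | 70.2% / 59.4% | 70.3–78.2% / 59.6–76.2% |
| Monotone, effect at last visit only | 70.2% / 59.4% | 70.3–71.1% / 59.6–61.2% |
| Full overlap | 77.6% / 75.1% | 77.7–78.8% / 75.1–77.4% |

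**4. Cost of an unstructured covariance.** It has 5×6/2 = 15 parameters. Take complete data and true compound symmetry, with the ANOVA at 80% power; the noncentrality is the same for both tests.

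- 15 per arm: the ANOVA refers to F(4, 112), and 80% power needs noncentrality 12.45. The size-correct unstructured test refers to F(4, 25) and has 73.2% power.
- 30 per arm: F(4, 232), noncentrality 12.18; the unstructured test, F(4, 55), has 77.0% power.
- An unscaled Wald F on Satterthwaite df is, on complete data at 15 per arm, (28/25)·F(4, 25) judged against F(4, 28). Its type I error is 7.5%. At 30 per arm it is (58/55)·F(4, 55) against F(4, 58), giving 6.1%.

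**5. Mixed model with compound symmetry, covariance estimated.** On complete data this gives the planned univariate interaction F. Simulation at 15 per arm, correlation 0.6, 10% missing per follow-up:

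- 400 trials per cell (Monte Carlo SE about 2 points): mixed model about 78–81% against 57–60% for completers with independent misses; 60–74% against 56–60% with monotone dropout; no type I inflation.
- A repeat with 2,000 trials per cell (SE about 1 point), REML, denominator df = observed values − participants − 8, effects last-visit-only, linear or constant: 74–79% against 57–58%, and 58–75% against 57–60%. Type I error for the mixed model was 4.5% and 5.3%. This larger run is the better guide, and it puts the independent-miss gain slightly lower.

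**The case against.** The strongest case on the other side accepts the omission but denies that it justifies changing the model. Repeated measures ANOVA is legitimate on complete data, and no missing visit is reported. An unstructured mixed model costs interaction power in a small trial even when nothing is missing (step 4). In a simulation at 15 per arm under compound symmetry (1,500 trials per cell), its size-calibrated power under monotone dropout was 61–68% against 69–71% for the completer ANOVA at 5% per follow-up, and 46–60% against 55–58% at 10%. That stands against unstructured covariance as the default. It does not stand against a mixed model with the ANOVA's own compound-symmetry covariance, which matched or beat the completer ANOVA (step 5). Compound symmetry was also the true structure in these comparisons, which favours both the ANOVA and the matching mixed model.

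A second objection is that the document calls itself a summary and is written in the past tense, so a fuller plan may exist. That is fair; none is among the documents.

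A reader might infer three stronger things that the documents do not support:

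- **That incomplete participants were dropped.** The plan names neither a procedure nor a rule, so this is an inference from usual SPSS practice.
- **That the result is biased.** Bias could arise if missingness depends on pain differently by arm, but nothing in the documents gives its size or direction.
- **That any mixed model is a free improvement.** It is not, for the reasons just given.

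**Conclusion.** The concern holds in a limited form and should be fixed. It is certain that the plan gives no analysis set and no missing-data rule. Loss of data and power, and a mismatch between the ANOVA and t-test populations, follow only if visits were missed and the ANOVA was run listwise.

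The loss cannot be sized for this trial. In the illustrations the mixed model's advantage on the interaction test runs from nothing (no missed visit), through almost nothing (full overlap, or monotone dropout with an effect only at the last visit), to roughly 15–20 points with 10% independent misses per follow-up. The documents do not settle which pattern applies; because follow-up runs through an unsupervised phase, monotone dropout is at least as plausible as scattered misses. All power figures rest on the assumed rates, covariances and effect shapes, and on data missing completely at random. Confidence is medium.

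**What to change.** State the analysis set and missing-data method, and report the number observed per arm and visit. Make the main analysis a linear mixed model (SPSS MIXED, REML) with group, visit and group-by-visit, baseline being one of the five visits. Include every observed value from all randomised participants in their allocated arm. Take the visit-specific group contrasts from this model, so that they share one population with the interaction test, and keep the completer ANOVA as a sensitivity analysis.

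Name the covariance before fitting. Compound symmetry preserves the planned interaction test when data are complete. Because it assumes sphericity, add a sensitivity analysis with a less restrictive structure. Use unstructured as the main choice only if the sample size supports it, and then with Kenward-Roger for the 4-df interaction test, not an unscaled Satterthwaite F; confirm that the SPSS version in use offers it.

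The cost is SAP wording and a different procedure in the same software, with no new data. The method relies on missing at random and does not remove bias if that fails. If the data are already analysed, label the result as a re-analysis.

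### Study 3: baseline is counted as an outcome visit and not used as a covariate, so the group main effect is diluted to four fifths and the per-visit t-tests lose precision

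*Combined protocol and SAP*

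**What the plan says.** The Study 3 protocol text says outcome assessments were "performed at five time points: Baseline, 2 weeks after the intervention, 4 weeks after the intervention, 1-month follow-up, 2-month follow-up". Both arms first receive the same physical therapy for 4 weeks. The assigned exercise comes after that: "Subsequently, they followed their assigned home-based exercise program three days a week for 4 weeks".

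The Study 3 Statistical Analysis Plan states: "Outcome measures were analyzed using two-way repeated measures ANOVA to examine" three effects. They are "Main effects of time (changes across assessment points"), "Main effects of group (differences between strengthening and stretching groups") and "Interaction effects (whether changes over time differed by group"). Bonferroni post-hoc tests follow, and then "Independent sample t-tests compared groups at individual assessment times".

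The plan does not exclude baseline from the time factor. It names no ANCOVA, baseline covariate or change score, and does not say which effect is the treatment comparison. That baseline is a level of the ANOVA is therefore an inference, but it is the natural one and nothing in the text contradicts it.

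**The concern.** The trial exists to compare strengthening with stretching, and the plan offers three routes to that comparison.

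- **Group main effect.** This averages the arm difference over all five visits. One of them precedes treatment and has expected difference zero under randomisation, so the average is pulled towards zero.
- **Per-visit t-tests.** These are not diluted, but they discard the baseline value, which usually explains part of the variation between patients.
- **Group-by-time interaction.** This uses baseline within patients and cancels a constant baseline imbalance. It is a 4-df omnibus test, so it gives neither a direction nor a size of effect.

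None of the three yields a baseline-adjusted difference between arms with a confidence interval. If the five-visit main effect were reported as the difference between arms, a real difference would be understated and a finding of no difference would become more likely.

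**Working it through.** **Inputs from the documents.** Five time points including baseline; two randomised arms; significance level 0.05 (taken as two-sided); no covariate. Study 3 states no sample size, SD, effect size, correlation or allocation ratio, so there is no planned figure to reproduce.

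**Step 1: dilution.** This needs no assumption about SD, n or correlation. The main effect is the mean of the five visit differences, with baseline expectation 0.

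| Pattern of effect over the five visits | Five-visit mean | Four post-baseline visits |
|---|---|---|
| 0, d, d, d, d | 0.8d | d |
| 0, 0.25d, 0.5d, 0.75d, d | 0.5d | 0.625d |
| 0, 0, 0, d, d | 0.4d | 0.5d |

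The factor due to baseline is 4/5 in every row. Any further shrinkage comes from later visits that carry little or no effect. The third row could arise if some visits fall before the assigned exercise, which the visit labels leave unclear.

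**Step 2: precision of the per-visit comparison.** With baseline-to-visit correlation r, the adjusted variance is 1 − r² times the unadjusted variance.

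| r (assumed) | 1 − r² | Variance cut | Extra patients the t-test needs, 1/(1 − r²) − 1 |
|---|---|---|---|
| 0.3 | 0.91 | 9% | 10% |
| 0.5 | 0.75 | 25% | 33% |
| 0.7 | 0.51 | 49% | 96% |

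**Step 3: power, as illustration only.** Assumed: 20 per arm, d = 0.6 SD, equal correlation r between all visits (compound symmetry), two-sided 0.05.

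Variances, with SD 1:
- five-visit mean: (1+4r)/5
- unadjusted mean of k post-baseline visits: (1+(k−1)r)/k
- adjusted mean of k visits: (1+(k−1)r)/k − r², on 2n−3 df

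These feed a noncentral t. The interaction uses a noncentral F with 4 and 4(2n−2) df and λ = (n/2)·Σ(d_t − d̄)²/(1−r).

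Example at r = 0.5, effect at all four visits:
- main effect: expectation 0.48, variance 0.60
- adjusted four-visit mean: expectation 0.60, variance 0.625 − 0.25 = 0.375
- interaction: λ = 10 × 0.288/0.5 = 5.76

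| Analysis | r=0.3 | r=0.5 | r=0.7 |
|---|---|---|---|
| *Effect at all four post-baseline visits* | | | |
| Planned main effect (five visits) | 0.61 | 0.48 | 0.40 |
| Planned interaction | 0.32 | 0.44 | 0.68 |
| Unadjusted four-visit mean | 0.76 | 0.65 | 0.56 |
| Adjusted four-visit mean | 0.85 | 0.85 | 0.93 |
| Single visit, planned t-test | 0.46 | 0.46 | 0.46 |
| Single visit, adjusted | 0.49 | 0.57 | 0.73 |
| *Effect at the last two visits only* | | | |
| Planned main effect (five visits) | 0.20 | 0.16 | 0.14 |
| Planned interaction | 0.47 | 0.63 | 0.87 |
| Adjusted four-visit mean | 0.32 | 0.33 | 0.41 |
| Adjusted mean of those two visits | 0.70 | 0.74 | 0.87 |

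At r = 0.5 with a constant effect, taking baseline out of the average raises power from 0.48 to 0.65, and adjusting for it raises power from 0.65 to 0.85.

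**Step 4: simulation check.** With 40,000 replicates per scenario, these powers agreed within 0.02. The mean five-visit estimates were 0.48 (constant effect) and 0.24 (late effect) for d = 0.6, which are 0.8d and 0.4d. Type I error of all these tests was 0.047 to 0.052.

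**The case against.** The strongest reply is that the interaction is already the treatment test: it asks whether change over time differs by arm, it uses baseline, and it is not diluted. This is largely right. With a late effect the interaction beats the adjusted four-visit mean at every r shown, and at r = 0.7 it equals the adjusted two-visit mean. Set against a joint 4-df adjusted test with unstructured covariance at 20 per arm, it loses little or nothing when the effect is late (about 0.63 for both at r = 0.5; 0.87 for the interaction against 0.84 at r = 0.7). Two points remain. The plan does not name the interaction as the treatment comparison, and the interaction gives no estimate.

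The second reply is that the precision gain rests on assumed correlations, and that equal correlation flatters adjustment. This also stands in part. If correlation decays with distance (AR(1), adjacent-visit r of 0.3/0.5/0.7), adjustment cuts last-visit variance by only about 0%, 0.4% and 6%. Even so, with a constant effect the adjusted four-visit mean has power 0.85/0.78/0.76, against 0.74/0.60/0.47 for the five-visit main effect.

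Third, the plan is written in the past tense, so the change may amount to a re-analysis. That affects how it must be labelled, not whether the point is right.

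**Conclusion.** The concern holds and should be fixed. The 4/5 dilution of the group main effect follows from randomisation and the list of time points, given that baseline is a level of the time factor. It is worse if some later visits precede the assigned exercise. The precision loss in the t-tests is real but of unknown size: negligible if baseline predicts the visit poorly, and about half the variance at r = 0.7. The power figures illustrate the issue under assumed inputs and are not estimates for this trial. The planned tests remain valid as to baseline handling. What is missing is an efficient, clearly defined estimate of the difference between arms.

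**What to change.** In the Study 3 Statistical Analysis Plan:

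1. Remove baseline from the outcome vector. Model post-baseline VAS and gait values with group, visit, group-by-visit and the baseline value of the same outcome as covariate.
2. Report the adjusted difference between arms with a 95% confidence interval at each visit, in place of the unadjusted t-tests, and averaged over a set of visits named in advance that fall after the assigned exercise has begun. State which of these is the main treatment comparison.
3. Do not present a five-visit group main effect as the treatment effect.
4. Reconcile the visit labels with the physical therapy and exercise phases, giving each visit in weeks from randomisation. The choice of visits to average depends on this, and with a late effect a poorly chosen average costs more power than adjustment gains.

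The cost is a change of wording and one degree of freedom for the covariate, with the same data and software. If the analyses have already been run, it is a re-analysis and should be reported as such.

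### Study 3 does not say which of its three kinds of group comparison answers strengthening versus stretching, and the group main effect averages in at least baseline; name one adjusted contrast over visits after exercise starts

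*Combined protocol and SAP*

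**What the plan says.** The question is in Study 3, Study Protocol: "It aimed to compare the effects of strengthening versus stretching exercises on individuals with PF". The treatment sequence follows: "Both groups initially received standardized conservative physical therapy (therapeutic ultrasound and manual therapy) twice a week for 4 weeks", then "Subsequently, they followed their assigned home-based exercise program three days a week for 4 weeks". Outcomes are measured at five points: "Baseline, 2 weeks after the intervention, 4 weeks after the intervention, 1-month follow-up, 2-month follow-up".

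Study 3, Statistical Analysis Plan, puts the outcomes into a two-way repeated measures ANOVA with three terms: "Main effects of time (changes across assessment points"), "Main effects of group (differences between strengthening and stretching groups") and "Interaction effects (whether changes over time differed by group"). It adds Bonferroni post-hoc tests to locate the time points that differ, and then: "Independent sample t-tests compared groups at individual assessment times".

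The section does not name a deciding comparison, a deciding visit or a primary outcome. It describes no adjustment for a baseline or other earlier value. It gives no sample size, effect size, SD or correlation for Study 3.

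**The concern.** Three kinds of test compare the arms, and they estimate different things:

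- **Group main effect:** the difference averaged over every level of the time factor, including any visit before the assigned exercise began.
- **Interaction:** asks only whether the profiles are parallel. With five time points it has 4 degrees of freedom and gives no single estimate or interval.
- **Visit-by-visit t-tests:** one answer per visit, without using each patient's earlier value.

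Because none is named as decisive, the answer can be taken from whichever test is significant, and the tests can disagree. If the group main effect were reported as the treatment effect, it would understate the mean difference between the exercise programmes. No planned term gives one undiluted, adjusted estimate with a confidence interval.

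**Working it through.** Study 3 states no design figure, so there is none to reproduce. The five visits and the order of treatments come from Study 3, Study Protocol. Everything marked assumed below is not in the documents.

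**1. Dilution of the group main effect.** Let k be the number of the five visits after the assigned exercise starts, with an expected difference of zero before it. The main effect is the average of the five visit differences, so its expectation is (k/5) × the mean difference after exercise starts.

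- Only baseline precedes exercise (k = 4): 4/5 = 80%.
- Baseline and the 2- and 4-week visits precede it (k = 2): 2/5 = 40%.
- If baseline is not a level of the time factor: 4/4 = 100% or 2/4 = 50%.

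These shares need no assumed sample size, SD or correlation.

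**2. Sample-size cost of the main effect** (assumed unit SD, compound symmetry with correlation ρ, constant effect after exercise starts).

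- Variance of the five-visit mean: (1 + 4ρ)/5.
- Variance of the mean after exercise starts: Vp = (1 + (k−1)ρ)/k.
- The same after adjusting for the last pre-exercise value: Va = Vp − ρ².
- Dilution factor: [(1 + 4ρ)/5] / (k/5)² / Vp. Adjustment factor: Vp/Va.
- Example, k = 4, ρ = 0.5: 0.6/0.64/0.625 = 1.50; 0.625/0.375 = 1.67; product 2.50.

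| k | Factor | ρ = 0.3 | ρ = 0.5 | ρ = 0.7 |
|---|---|---|---|---|
| 4 | Dilution | 1.45 | 1.50 | 1.53 |
| 4 | No adjustment | 1.23 | 1.67 | 2.72 |
| 2 | Dilution | 4.23 | 5.00 | 5.59 |
| 2 | No adjustment | 1.16 | 1.50 | 2.36 |

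With k = 4 and ρ of 0.5 or more, the missing adjustment costs more than the dilution.

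**3. Chance of some significant group result when there is no effect** (simulation; assumed normal data, 20 or 30 per arm, ρ 0.3-0.7, two-sided 0.05, one outcome). A result counts if the main effect, the interaction or an eligible t-test is significant.

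| Tests counted | Chance |
|---|---|
| Main effect, interaction, four post-baseline t-tests, uncorrected (k = 4) | about 16-20% |
| Main effect, interaction, two t-tests after exercise starts, uncorrected (k = 2) | about 13-16% |
| Main effect, interaction, five t-tests under Bonferroni | about 10-12% |
| Main effect and interaction only | about 10% |
| One named adjusted contrast | about 5% |

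**4. Power against the interaction** (assumed 30 per arm, mean effect 0.6 SD, k = 4, ρ = 0.3/0.5/0.7). The interaction uses a noncentral F on 4 and 4(2n−2) degrees of freedom, with λ = (n/2)Σ(d_t − d̄)²/(1−ρ).

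- Adjusted contrast: 0.95/0.96/0.99.
- Interaction, constant effect: 0.47/0.63/0.87.
- Interaction, linear build-up (0, 0.24, 0.48, 0.72, 0.96): 0.81/0.93/0.995.

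**The case against.** The best defence is that the interaction already addresses the question. It uses baseline, visits before exercise do not bias it, and under a linear build-up with high correlation it is as powerful as the proposed contrast. The main effect is a standard ANOVA term that the plan merely lists. All of that stands. It does not supply a single estimate, and the plan does not make the interaction decisive.

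Four stronger readings are tempting, and the documents do not support them.

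- **That several pre-exercise visits are certainly averaged in.** Only baseline is certain to precede exercise. The 2- and 4-week visits are described as following the intervention, without saying whether that means the common physiotherapy or the exercise. The 40% share and the four- to six-fold dilution cost apply to one reading only.
- **That the plan will report the main effect as the treatment effect.** Nothing says so. Nor is the direction of distortion fixed if the target is the 2-month difference. With k = 4 the main effect is 0.48/0.96 = 50% of it under a linear build-up, and 0.48/0.24 = 200% under a linear fade.
- **That the error rate is 18-23%.** That figure counts all seven group tests, including the t-test at baseline, which nobody could present as a treatment effect.
- **That the t-tests are clearly uncorrected.** The Bonferroni sentence comes immediately before the t-test sentence. It may concern only comparisons between time points, or it may cover the t-tests. Both readings are shown above.

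The document is headed as a summary and written in the past tense, so fuller timing may exist elsewhere and the data may already have been analysed. This limits what the change can achieve; it does not supply the missing choice.

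**Conclusion.** The concern holds in this form: the plan names no deciding group comparison and gives no clear visit clock, and one of the listed comparisons is diluted if baseline is a level of the time factor, as the wording of the time effect implies. The main effect then has 80% or 40% of the mean difference after exercise starts, depending on the visit clock.

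The error rates, sample-size factors and power values are illustrative, because Study 3 gives none of their inputs. On those assumptions, leaving the choice open raises the chance of a false positive group result from about 5% to between 10% and 20% per outcome. The case for change rests on having one interpretable estimate and one decision rule. It does not rest on a guaranteed power gain, which depends on the shape of the effect and can be nil. The sponsor should make the change; confidence is medium because of the unclear timing and the summary format.

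**What to change.** 1. State each visit in weeks from randomisation and mark when the assigned exercise starts. This comes first: adjusting for a value taken after that start would remove part of the effect.
2. Name as the treatment comparison the mean strengthening-minus-stretching difference over the visits after that start, adjusted for the last value before it, by ANCOVA or a mixed model with that contrast, with a 95% CI. If the end effect matters more than the average, name the 2-month visit instead, with the same adjustment.
3. Keep the interaction and the t-tests at visits after exercise starts as secondary, say whether Bonferroni covers those t-tests, and do not read the group main effect as the treatment effect.
4. If outcome data have already been seen, report the contrast beside the planned ANOVA and label it post hoc.

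The cost is analysis-plan wording and one sentence on timing. No new visits or data are needed, and SPSS can fit the model. Visits in the common physiotherapy phase would no longer count towards the treatment comparison, and a post hoc contrast would be weaker as confirmatory evidence.
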